9.5.4.2 Sample Integrity

A sample integrity sub-group analysis will be conducted among only the samples collected on or after December 10th, 2024, the date at which updated sample collection instructions were implemented. The same sample integrity criteria used for the primary endpoint (volume, hemolysis, and clotting) will be summarized using frequencies and percentages by time point, collection method, and cohort.

This sub-group analysis will be conducted in the PPS.

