6.3.2 Per-Protocol Set (PPS)

The PPS will include all participants who successfully completed at least five Tasso+™ administrations and do not have any important protocol deviations. This analysis set will be used for sensitivity analyses.

If the FAS and PPS include the same set of participants, only one set of analyses will be produced.

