9.5.2 Primary Endpoints

9.5.2.1 Sample Integrity

Descriptive statistics will be presented for the FAS and PPS to summarize the proportion of Tasso+™/SST and Tasso+™/EDTA samples collected on Day 1 for each cohort and on each of Days 29 and 57 for Cohorts A and B combined with the following attributes:

- Adequate volume, defined as at least 300 µL
- Without moderate or gross hemolysis, as defined by Central Laboratory SOP (see Table “Impact of Varying Degrees of Hemolysis” in [Section 6.3.1](#) of the protocol)
- Adequate volume and without moderate or gross hemolysis (for SST samples)
- Without clotting (for EDTA samples only)
- Adequate volume, without moderate or gross hemolysis, and without clotting (for EDTA samples only)

Sample integrity data will be analyzed using the laboratory vendor data for all subjects and visits with the exception of Cohort B Day 1 records, which were collected in the electronic data capture (EDC) system.

Statistical Analysis Plan (SAP)

Protocol: Phase 1 Study Evaluating Technologies for Point-of-Care Blood Collections in Support of Decentralized Outpatient Assessments in Pandemic and Clinical Trial Settings

Version Date: 27-Jun-2025

Sponsor: Resilience Government Services, Inc.

Protocol No: 5309/0024

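### The change in collection instructions on 10 December 2024 is examined only through post-change samples in the per-protocol set, with no full-analysis-set version and no pre-change column

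*SAP*

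**What the plan says.** SAP 9.5.2.1 sets out the primary integrity analysis: "Descriptive statistics will be presented for the FAS and PPS to summarize the proportion of Tasso+™/SST and Tasso+™/EDTA samples collected on Day 1" by cohort, and "on each of Days 29 and 57 for Cohorts A and B combined with the following attributes". The attributes are volume, hemolysis and, for EDTA tubes, clotting. Nothing in that section splits or adjusts by collection date.

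SAP 9.5.4.2 is the only place in either document that mentions a change in the instructions: "A sample integrity sub-group analysis will be conducted among only the samples collected on or after December 10th, 2024", which is "the date at which updated sample collection instructions were implemented". The same criteria "will be summarized using frequencies and percentages by time point, collection method, and cohort", and "This sub-group analysis will be conducted in the PPS". The content of the update is not described.

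SAP 6.3.2 defines the PPS as "all participants who successfully completed at least five Tasso+™ administrations and do not have any important protocol deviations" and assigns it to sensitivity analyses. SAP 6.3.1 makes the FAS the primary set for the primary endpoint. The protocol summary plans two self-administrations on each of Days 1, 29 and 57, so six per participant.

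**The concern.** The reader who wants to know how the device performs under the current instructions has one table to go to, and it has two weaknesses.

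- **Selection.** Membership of the PPS depends on a count of successful administrations, which may lie close to the outcome being tabulated. A high post-change percentage could then come partly from who was kept. The count also runs over all three visits. A participant with two failures on Day 1 under the old instructions can reach only four of the six planned, and so loses the four later samples even if they were taken under the new instructions.
- **No printed contrast.** The table shows one period only. The FAS, which carries the primary result, gets no breakdown by period at all.

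If the instructions mattered, the pooled primary percentage is a mixture of two procedures. The report would then hold no unselected figure for the procedure now in use.

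**Working it through.** **Inputs.** About 200 participants at 2:1 (SAP 6.1, 6.2); six planned administrations (protocol summary); at least five successes for the PPS (SAP 6.3.2). The documents do not give the share of samples by period, the effect of the update, or the meaning of a successful administration. These are assumed below and shown as ranges.

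**1. The plan's own figure.** 200 × 2/3 = 133.3 and 200 × 1/3 = 66.7, which matches the planned 133 and 67. No power calculation is stated, so there is none to check.

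**2. Possible selection in the PPS.** Assume that success is the same event as the reported outcome, that the six uses are independent, and that each succeeds with probability p. Then P(5 of 6) = 6p⁵(1 − p) and P(6 of 6) = p⁶. The expected success rate among those kept is

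[5 × 6p⁵(1 − p) + 6 × p⁶] / {6 × [6p⁵(1 − p) + p⁶]} = (5 − 4p)/(6 − 5p).

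| True rate p | Share kept in PPS | Rate seen in PPS |
|---|---|---|
| 60% | 23.3% | 2.6/3.0 = 86.7% |
| 70% | 42.0% | 2.2/2.5 = 88.0% |
| 80% | 65.5% | 1.8/2.0 = 90.0% |

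With a constant p, the post-change subset has the same expected rate, so these figures would appear with no effect of the new instructions. This is the strong end of the range. If success means only that device use was completed, the inflation could be small. If it means adequate blood, volume is selected directly, but hemolysis and clotting are not. A repeat kit (protocol 4.3) would also loosen the six-use count.

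**3. What the planned tables already allow.** SAP 9.5.2.1 gives PPS totals for all samples, and SAP 9.5.4.2 gives the post-change part in the same set. Pre-change PPS = total − post-change, directly by cohort on Day 1, and after summing cohorts on Days 29 and 57. For the FAS only the total is planned, so the subtraction is not possible.

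**4. Size of the mixture.** With a share f of samples before the change, and rates p0 before and p1 after, pooled = f·p0 + (1 − f)·p1. The gap to the post-change rate is f × (p1 − p0).

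| Assumed difference | f = 25% | f = 50% | f = 75% |
|---|---|---|---|
| 0 points | 0 | 0 | 0 |
| 10 points (80% to 90%) | 2.5 | 5.0 | 7.5 |
| 23.4 points (70.0% to 93.4%) | 5.9 | 11.7 | 17.6 |

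The last row borrows success rates from two different studies cited in protocol 1.2. They are not a before/after pair and serve only as a wide case.

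**5. Precision of a side-by-side table.** Each participant gives one scheduled sample per visit and tube type, so within such a cell the two periods contain different people. The Wald 95% half-width of the difference is 1.96 × √[p0(1 − p0)/n0 + p1(1 − p1)/n1]. At 70.0% and 93.4%, for f = 25%, 50% and 75%:

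- all 200: 13.3, 10.2 and 10.1 points
- Cohort A, Day 1 (133): 16.4, 12.5 and 12.3 points
- Cohort B, Day 1 (67): 22.8, 17.7 and 17.3 points

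**The case against.** The strongest reply is that little is broken. Three stronger readings are tempting, and the documents do not support them.

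- A reader might infer that pooling the two periods makes the primary analysis wrong. It does not. Protocol 3.1 and 9.4.1.1 define the endpoint over all samples, and protocol version 3.0, dated 17 January 2025, kept that definition after the change.
- A reader might infer that no comparison is possible. Within the PPS it is, by the subtraction in step 3. What is missing is the printed column and any FAS counterpart.
- A reader might infer that the post-change figure is bound to be inflated. Success is undefined in the current SAP, so the amount is unproven. The definition in the SAP document history is superseded text and cannot be relied on.

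Two further points stand. No first-collection date is given, so the existence of pre-change samples is inferred from the reference to updated instructions and from the restriction to later samples. Also, the study is descriptive, and a calendar split is not randomised; an interval of about 17 to 23 points either way in Cohort B could invite over-reading.

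The objection does not justify the choice of set. The SAP makes the FAS primary for this endpoint and the PPS a sensitivity set, yet here the PPS stands alone.

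**Conclusion.** The point holds as a cheap improvement to one exploratory table. The only planned view of performance under the current instructions is in a set chosen partly on successful use, and the primary set has no breakdown by period.

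The possible inflation runs from small to large: up to 26.7 points at a true rate of 60% (86.7 − 60), 18.0 at 70% and 10.0 at 80%, and those upper values need success to equal the outcome and the six uses to be independent. The gap between the pooled primary and the post-change rate depends on a share and an effect that the documents do not give; it is zero if the instructions made no difference. Neither range is an estimate of what this trial will show.

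**What to change.** In SAP 9.5.4.2:

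1. Make the FAS the main set and keep the PPS as sensitivity.
2. Show integrity before 10 December 2024 and on or after it, side by side, within visit and tube type, and by cohort on Day 1. Give counts, percentages and descriptive 95% confidence intervals.
3. Quote the post-change FAS figure beside the pooled primary result, which stays as it is.
4. Label the comparison as non-randomised and confounded with calendar time.
5. State in a sentence what the update changed.

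The cost is SAP wording and one period variable on data already collected. The downside is small cells, especially Cohort B on Day 1, where the counts should be read before any difference.

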9.5.4.3 Testing Accuracy

A stratified testing accuracy analysis will be conducted using the following two strata:

- Samples received by the central laboratory \leq 1 day after collection (ie, received by the central laboratory either on the same day as collection or the day following collection)
- Samples received by the central laboratory $>$ 1 day after collection

Contingency correlation coefficient will be computed to estimate the extent of the relationship between the venipuncture collection and the Tasso+™ collection at Day 1 by cohort for each biochemistry parameter.

This stratified analysis will be conducted in the PPS.

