6.3.2 Testing Accuracy

Testing accuracy of the Tasso+™ device, as part of device performance, will be evaluated as (i) the correlation of SARS-CoV-2 serology between venipuncture and either Tasso+™/SST or Tasso+™/EDTA samples collected on Day 1; and (ii) the correlation of each chemistry analyte between venipuncture and Tasso+™/SST samples collected on Day 1. This endpoint will only be assessed on Day 1 for each cohort separately.

Seroconversion will be evaluated using IgG Nucleocapsid assay. A total serum (SST) or plasma (EDTA) volume of 175 µL will be necessary to cover potential retesting, if needed. Any participant who is positive for IgG Nucleocapsid assay for either matrix (SST or EDTA), will be considered SARS-CoV-2 positive.

The following chemistry analytes will be assessed for correlation between the two collection approaches (venipuncture and Tasso+™/SST) on Day 1: sodium, potassium, chloride, blood urea nitrogen, creatinine, glucose, phosphate, uric acid, and C-reactive protein.

Noteworthy, in case of long duration between sample collection and testing, there may be risks associated with inaccurate sodium, potassium, and glucose values.

If a sodium, potassium, or glucose level is determined by the PI to be possibly clinically significant, a venipuncture repeat of the test should be performed at the Investigator site for safety reasons. Testing will be performed by the Investigator site and will not be sent to the Central laboratory.

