7.4 Instruction for Use

The section below provides an overview of the IFU. The detailed IFU will be provided in a separate document. Instructional video is available on Tasso Inc. website (<http://www.tassoinc.com/tassoplus-video>). The use of Tasso+™ kit is not intended for use in diagnostic procedures.

The Tasso+™ kit includes the sterile, disposable Tasso+™ blood lancing device, and the supplies necessary to administer the device.

When collecting a sample, the device will be held onto the skin by a mild adhesive. With a press of the button, a sterile lancet will puncture the skin, simultaneously creating a slight vacuum that will help capillary blood flow under gravity into a compatible tube. After a predefined time period, or when the tube is full, the device will be peeled off the skin. The tube will be removed and capped for shipment. The lancet is single use and automatically retracts into the device in a safe position after use.

Preparation steps notably include set-up of the participant, identification of the collection sites, insertion of applicable tube (SST or EDTA) into the device, and warming and cleaning of the collection site.

Collection step notably includes sticking of the device to collection site, activation of the lancet, filling of the tube, removal of the device, closure of the tubes, and inversion of the tubes.

Shipping and final steps notably include writing of participant's ID number on tube, placing of tube in return bag, recording of the time and date of collection, packaging and shipping of tubes to the Central Laboratory, and discarding of leftover material (excepting Tasso+™).

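### The exploratory shipping-delay analysis pools every delay above one day and cannot show how the Tasso+ minus venous difference changes with time to receipt

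*SAP*

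**What the plan says.** Protocol 6.3.2 warns that "in case of long duration between sample collection and testing, there may be risks associated with inaccurate sodium, potassium, and glucose values". It gives no drift per hour or per day.

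Among the exploratory endpoints, SAP 9.5.4.3 takes up transit time: "A stratified testing accuracy analysis will be conducted using the following two strata". The first stratum holds samples "received by the central laboratory either on the same day as collection or the day following collection". The second is "Samples received by the central laboratory $>$ 1 day after collection", with no upper limit and no further split. Within the strata, "Contingency correlation coefficient will be computed to estimate the extent of the relationship" between the two collection methods, "at Day 1 by cohort for each biochemistry parameter". The section ends: "This stratified analysis will be conducted in the PPS". It sets no minimum stratum size and plans no confidence interval and no analysis by day or hour.

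SAP 9.5.1 states that hypothesis testing does not apply, and SAP 6.1 gives no formal basis for the sample size. Protocol 7.4 includes "recording of the time and date of collection" in the instructions for use. Neither document says whether the clock time of receipt is recorded.

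**The concern.** The protocol's worry is graded: the longer the delay, the less some analytes can be trusted. The planned analysis replaces that scale with one yes/no split. It puts a tube received 2 days after collection with one received after 4 days. It then divides by cohort, so a stratum may hold only a handful of participants.

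For a device meant to support decentralised collection, the useful result is how far capillary values move from venous values as transit lengthens. Two coefficients, one per stratum, cannot give that.

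**Working it through.** **Inputs.** Planned cohort sizes are 133 and 67 (SAP 6.2). The arithmetic agrees: 200 × 2/3 = 133.3 and 200 × 1/3 = 66.7. The documents give no power, alpha, effect size or stratum size for this analysis, so there is no planned figure to reproduce. They also give no distribution of delay, so the shares below are assumptions shown as a range.

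**1. Size of the later stratum.** Expected n = cohort n × share received after more than 1 day. P(≤5) is the binomial chance of five or fewer such samples.

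| Share > 1 day | Cohort A, n | Cohort A, P(≤5) | Cohort B, n | Cohort B, P(≤5) |
|---|---|---|---|---|
| 5% | 133 × 0.05 = 6.7 | 34% | 67 × 0.05 = 3.4 | 88% |
| 10% | 133 × 0.10 = 13.3 | 0.7% | 67 × 0.10 = 6.7 | 33% |
| 20% | 133 × 0.20 = 26.6 | about 0% | 67 × 0.20 = 13.4 | 0.4% |

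These are upper figures. The per-protocol set requires at least five successful administrations and no important deviation (SAP 6.3.2), so it may be smaller than the randomised cohorts.

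As a guide to precision only, take the Fisher interval tanh(atanh r ± 1.96/√(n−3)) for a Pearson correlation with r = 0.95. It runs 0.93-0.96 at n = 133, 0.84-0.99 at n = 13 and 0.69-0.99 at n = 7.

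**2. Information kept by the cut.** Suppose the paired difference drifts linearly with delay D in whole days. Comparing the two strata then keeps a fraction corr(D, 1{D>1})² of the information in a linear trend.

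Worked case: 70/15/10/5% received at 1/2/3/4 days.
- Mean of D = 0.70 + 0.30 + 0.30 + 0.20 = 1.5.
- Variance of D = 0.70 × 0.25 + 0.15 × 0.25 + 0.10 × 2.25 + 0.05 × 6.25 = 0.75.
- Variance of the indicator = 0.3 × 0.7 = 0.21.
- Covariance = 0.80 − 1.5 × 0.3 = 0.35.
- Fraction kept = 0.35² / (0.75 × 0.21) = 0.78.

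To put this on a familiar scale, take a drift that a trend test would detect with 80% power at two-sided 0.05. The split then has power Φ(2.802 × √0.78 − 1.960) ≈ 70%. This is a yardstick for information, since the SAP plans neither test.

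| Assumed pattern (days to receipt) | Fraction kept | 80% becomes |
|---|---|---|
| 1/2: 80/20% | 1.00 | 80% |
| 1/3/4: 80/10/10% | 0.95 | 78% |
| 1/2/3: 95/3/2% | 0.89 | 75% |
| 1/2/3/4: 70/15/10/5% | 0.78 | 70% |
| 1/2/3/4: 50/20/20/10% | 0.74 | 68% |
| 0/1/2/3/4: 5/80/10/3/2% | 0.71 | 65% |
| 1/2/3/4: 10/40/30/20% | 0.34 | 37% |

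The loss on this yardstick runs from 0 to 43 points. In the last pattern the early stratum is the small one: 13 in Cohort A and 7 in Cohort B.

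**3. What a coefficient per stratum can show.** A measure of association does not give the size or direction of a difference. Take venous values with SD 0.35 and independent error with SD 0.10 (assumed). Pearson's r is then 0.35/√(0.35² + 0.10²) = 0.96 whatever constant is added to every capillary value. Making delay continuous therefore helps only if the outcome becomes the paired difference.

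**The case against.** The strongest reply is that this is an exploratory, descriptive display with no decision rule attached, and that nothing is tested. That stands. A reader might infer that the plan loses a definite amount of power to detect drift, but the documents do not support this. Simulating delay in hours, with late samples arriving at 2, 3 and 4 days in a 60/25/15% mix, gives a loss of 10 to 21 points. Both sides of that comparison are analyses the SAP does not contain, and the mix is assumed. Against whole days, the loss is zero if every late sample arrives on day 2.

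A reader might also infer that the strata overlap in true elapsed time. Calendar-day wording allows it: the early stratum could reach almost 48 hours and the later one could start just above 24. Day 1 samples are collected in the clinic, however. With collection at 08:00-17:00 and receipt at 09:00-17:00 (assumed), early delays are at most 33 hours and later ones at least 40, so there is no overlap.

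Two further limits stand. The randomised Cohort A versus B contrast already addresses the timing of centrifugation (Protocol 1.2), so the gap concerns length of transit only. In Cohort B, Day 1 Tasso+ and venous tubes are both spun at the site before shipping (Protocol 4.2.4), so there is less reason to expect their difference to drift. Finally, the documents do not report that delays of 2 to 4 days occurred.

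None of this lets two pooled strata answer how the difference changes with delay.

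**Conclusion.** The point holds as a cheap improvement to an exploratory analysis. It does not threaten a primary result. By its own definition, SAP 9.5.4.3 pools all delays above one day, splits again by cohort and gives no measure of change with delay. If 5-10% of samples take more than 1 day, the later stratum has about 7-13 participants in Cohort A and 3-7 in Cohort B, before per-protocol exclusions. The share of trend information kept runs from 0.34 to 1.00 over the patterns tried. That range rests on assumed delay distributions and a linear drift, so no single figure for the loss can be claimed. The question bears mainly on Cohort A, whose Day 1 Tasso+ tubes travel unspun.

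**What to change.** In SAP 9.5.4.3, for each of the nine chemistry analytes, regress the paired Day 1 Tasso+ minus venipuncture difference on days from collection to Central Laboratory receipt. Use hours if the vendor file holds the receipt time. Make Cohort A the main analysis and show Cohort B as a comparison. Report the slope with a 95% CI and a scatter plot of difference against delay. Keep the two strata as a descriptive display with n per stratum.

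The cost is a wording change and one simple model per analyte in each cohort, using dates already needed to form the strata. There are three limits:
- A linear trend is assumed, which the plot lets readers check.
- The slope stays imprecise if few tubes arrive late.
- Receipt stands in for testing, which is the interval named in Protocol 6.3.2.

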9.5.4.4 Percentage of Subjects with Complete Analyte Profile

The frequency and percentage of subjects who met the following criteria will be summarized by time point in the PPS:

- Had all of their biochemistry analytes resulted at the given time point (for SST)
- Had their SARS-CoV-2-IgG sample resulted (for SST)
- Had all of their biochemistry analytes and SARS-CoV-2-IgG sample resulted (for SST)
- Had their SARS-CoV-2-IgG sample resulted (for EDTA)

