4.2 Steps to the Process

4.2.1 *Training*

Training will be provided on Days 1 and 29 and will include detailed IFU and online video training. The detailed IFU will be provided in a separate document, and an overview of IFU is provided in [Section 7.4](#). When administering the Tasso+™ remotely, participants will receive proctor-support from the Site on Day 29 (and as requested, on Day 57) during working hours, the intent being to guide the participant through the process and to help troubleshoot should any difficulties be encountered. Training on Day 57 should be performed only if it is specifically requested due to participant hesitation.

4.2.2 *Blood Collection*

Once trained, and by following the IFU provided (see [Section 7.4](#)), participants will self-administer the Tasso+™ device in the Clinic at the Investigator site (supervised) and subsequently remotely, ie, at home or a suitable remote location (proctor-supported on Day 29 and unsupported on Day 57). Self-collection may be additionally supported on Day 57 using a proctor session, as requested, to guide the participant through the process and help to troubleshoot any difficulties. The SST tube will be preferably collected from the left upper arm and the EDTA tube will be preferably collected from the right upper arm.

As per IFU, participants will have to gently invert the Tasso+™ capillary collection tubes after the full collection process is completed.

4.2.3 *Blood Volume and Clotting Analyses*

Blood volume and clotting analyses will be assessed before centrifugation. Thus, for Cohort B, on Day 1, these endpoints will be assessed by the Site, while for Cohort A, on Day 1 and for Cohorts A and B combined on Days 29 and 57, these endpoints will be assessed by the Central Laboratory (see [Section 6.3](#)).

4.2.4 *Centrifugation*

Tasso+™ blood samples of participants randomized to Cohort A, collected on Day 1, will be centrifuged upon receipt by the Central Laboratory, as per the real-world use of Tasso+™.

Tasso+™ blood samples of participants randomized to Cohort B, collected on Day 1, will be centrifuged and aliquoted by the Site before shipping, following the same procedure as for venipuncture blood samples.

Tasso+™ blood samples of participants from both Cohorts A and B, collected on Days 29 and 57, will be centrifuged upon receipt by the Central Laboratory, as per the real-world use of Tasso+™.

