6.2 Randomization

Each participant will have a unique subject screening number obtained from the interactive voice response system (IVRS). Once the participant is deemed eligible, the participant will be assigned a randomization number.

Randomization will be performed via a centralized IVRS. On Day 1, eligible participants will be assigned to either Cohort A or Cohort B in a 2:1 ratio. Thus, it is planned to randomize approximately 133 participants into Cohort A and approximately 67 participants into Cohort B.

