9.5.4.5 Summary of Collected Sample Volume

Boxplots will be produced to visualize the volume of sample collected for each subject by time point and collection method (SST or EDTA). The x-axis of the boxplot will be split by cohort (for Day 1 only), with two boxplots for each cohort (one for SST and one for EDTA). Day 29 and Day 57 boxplots will summarize all subjects combined, with one boxplot for SST and one boxplot for EDTA. The figure will be produced for the PPS.

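### SAP 9.5.4.4 reports complete analyte profiles by time point with no cohort split, so the Day 1 percentage mixes two processing routes and is not like-for-like with Days 29 and 57

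*SAP*

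**What the plan says.** SAP 9.5.4.4 sets out four criteria: all biochemistry analytes resulted (SST), SARS-CoV-2 IgG resulted (SST), both of these together (SST), and IgG resulted (EDTA). The stated breakdown is: "The frequency and percentage of subjects who met the following criteria will be summarized by time point in the PPS". Cohort is not mentioned. The general conventions in SAP 9.0 contain no default rule to present results by cohort.

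The cohorts differ in how the Day 1 Tasso+ tubes are processed (Protocol 4.2.4):

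- Cohort A tubes "collected on Day 1, will be centrifuged upon receipt by the Central Laboratory, as per the real-world use of Tasso+™".
- Cohort B tubes "collected on Day 1, will be centrifuged and aliquoted by the Site before shipping, following the same procedure as for venipuncture blood samples".
- For both cohorts, tubes "collected on Days 29 and 57, will be centrifuged upon receipt by the Central Laboratory".

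SAP 6.2 gives the allocation: "On Day 1, eligible participants will be assigned to either Cohort A or Cohort B in a 2:1 ratio", so that "it is planned to randomize approximately 133 participants into Cohort A and approximately 67 participants into Cohort B".

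The other summaries of Day 1 sample quality or accuracy separate the cohorts. SAP 9.5.2.1 and 9.5.2.2 do so for the primary endpoints, and SAP 9.5.4.3 does so for the stratified accuracy analysis. In SAP 9.5.4.2 the integrity criteria "will be summarized using frequencies and percentages by time point, collection method, and cohort". SAP 9.5.4.5 states "The x-axis of the boxplot will be split by cohort (for Day 1 only", and shows Days 29 and 57 for all subjects together.

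**The concern.** A table laid out by time point invites the reader to look along the row from Day 1 (clinic) to Days 29 and 57 (home). In this table the processing route changes along that row as well as the setting: Day 1 blends site-spun and centrally spun tubes, while the home visits are all centrally spun. Any effect of processing on whether results come back is then folded into the visit-to-visit difference.

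Protocol 1.2 says the Day 1 cohort contrast is there to evaluate the timing of centrifugation. This is the one planned summary of whether a collection yields a complete set of results, and here that randomised contrast is not shown.

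The route from processing to a missing profile is most plausible for the two criteria that require every biochemistry analyte. Table 5 in Protocol 6.3.1 has moderate hemolysis invalidating potassium and phosphate, and losing either one fails the criterion. The two serology-only criteria are less exposed, because moderate hemolysis leaves serology unaffected and only gross hemolysis invalidates it.

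**Working it through.** **Inputs from the documents.** About 200 participants, allocated 2:1, planned as 133 in Cohort A and 67 in Cohort B (SAP 6.2). Processing routes as in Protocol 4.2.4.

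**Check of the plan's own figure.** 200 × 2/3 = 133.3 and 200 × 1/3 = 66.7, which round to the stated 133 and 67.

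**Assumed inputs.** Let pA and pB be the Day 1 complete-profile rates in Cohorts A and B. The documents give neither, so a range is shown.

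**Pooled Day 1 rate.**

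(133 × pA + 67 × pB) / 200 = 0.665 × pA + 0.335 × pB

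**Apparent change from pooling alone.** Suppose home collection has no effect of its own and the cohorts are otherwise comparable. All Day 29 and 57 tubes follow the Cohort A route, so the home rate is pA in both cohorts. The gap between the Day 1 figure and the home figure is then

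(0.665 × pA + 0.335 × pB) − pA = 0.335 × (pB − pA)

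| pA (assumed) | pB (assumed) | Pooled Day 1 | Home rate, no home effect | Apparent change, Day 1 to home |
|---|---|---|---|---|
| 70% | 70% | 70.0% | 70% | none |
| 70% | 80% | 73.35% | 70% | fall of 3.35 points |
| 80% | 95% | 85.03% | 80% | fall of 5.03 points |
| 70% | 90% | 76.7% | 70% | fall of 6.7 points |
| 50% | 90% | 63.4% | 50% | fall of 13.4 points |
| 90% | 70% | 83.3% | 90% | rise of 6.7 points |

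**Sensitivity to the per-protocol mix.** The table uses the per-protocol set (SAP 6.3.2: at least five successful administrations and no important deviations), whose cohort shares are unknown. For a 20-point difference in favour of Cohort B:

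- Cohort B share 60/150 = 40%: 0.20 × 0.40 = 8.0 points
- Cohort B share 50/110 = 45.5%: 0.20 × 0.455 = 9.1 points

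**After the change.** With Day 1 shown by cohort, Cohort A Day 1 (pA) sits beside a home rate produced by the same route, and the pooling term is zero. Precision remains usable. At 70% with n = 133 the 95% half-width is 1.96 × √(0.7 × 0.3 / 133) = 7.8 points; at 90% with n = 67 it is 1.96 × √(0.9 × 0.1 / 67) = 7.2 points. Both will be wider if the per-protocol set is smaller than planned enrolment.

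**The case against.** **Silence is not a decision to pool.** Where the SAP means to combine the cohorts it says so (9.5.2.1, 9.5.4.5), and table shells, which are not among the documents, might already split Day 1. This stands in part: nothing shows that the sponsor deliberately chose to pool. But the section does state its breakdown, and it is by time point. This SAP names cohort where it wants a split, and no default supplies one. An analyst following the text would produce a single Day 1 column. SAP 9.5.4.1 is also silent on cohort, but it concerns Day 57 only, when both cohorts share one route.

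**No clinic-to-home comparison is planned.** This is correct: the table is descriptive and SAP 9.5.1 rules out hypothesis testing. The comparison is nevertheless the natural reading of percentages set out by visit.

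**The mechanism is uncertain.** Blood volume is assessed before centrifugation, so a collection shortfall does not come from the processing route. Protocol 6.3.2 describes delay as making sodium, potassium and glucose inaccurate, not absent. The SAP does not say whether an invalidated value still counts as resulted; if it does, the hemolysis route closes. These points limit how likely a cohort difference is. They do not exclude one for the all-analyte criteria.

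**Processing effects are visible elsewhere.** Day 1 hemolysis, clotting, volume and correlations are all reported by cohort. That is true; what is lost is the completeness rate by cohort.

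A reader might also infer that Day 1 will look falsely good and home collection falsely poor. The documents do not support that: they give no rates, and the direction depends on which cohort does better.

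**Conclusion.** The point holds as an inconsistency in presentation with a quantifiable consequence. As written, SAP 9.5.4.4 yields a Day 1 percentage that mixes two randomised processing routes and sets it beside single-route home visits. About one third of any difference between the cohorts, 0.335 × (pB − pA), would appear as a change between Day 1 and home. Across the assumed rates above, that runs from a false fall of 13.4 points to a false rise of 6.7 points, and is zero if the rates are equal.

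The size rests on assumed rates and on the per-protocol set keeping the randomised 133:67 mix. The interpretation as a pure artefact rests on there being no true home effect. It would be wrong to infer that any observed change must be processing alone: supervision moves from Site staff to a remote proctor (optional on Day 57), and the shipper from Site to participant. It would also be wrong to infer that a main result is at risk. The table is exploratory and descriptive, and no primary or secondary result changes.

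**What to change.** In SAP 9.5.4.4, specify that each of the four criteria is presented by cohort on Day 1 and for Cohorts A and B combined on Days 29 and 57, matching 9.5.2.1 and 9.5.4.5. State that Cohort A on Day 1 is the processing-matched reference for the home visits, with a table note that supervision and shipper still differ between clinic and home. If the table shells already split Day 1, the SAP text should say so.

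The cost is one sentence in the SAP and an extra Day 1 column in one table. It needs no new data and uses the groups the trial already randomises.
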